10.1 Study monitoring

The monitoring visits will enable the sponsor or the monitor acting on his behalf, to assess the study's progress status, to verify the exactness and degree of completeness of the CRFs, to ensure that protocol as well as local regulations are being followed and that the investigator is fulfilling his obligations. Monitoring visits will also enable to correct errors in the CRFs compared to the source documents. The investigator will authorize the monitor, at a mutually convenient time during the study and after its end, to periodically review all of the CRFs and the related parts of administrative, medical and laboratory files of each participant in the study. The CRFs must be filled out before the monitoring visits.

10.2 Audits

During the study, people belonging to the sponsor quality assurance group may visit the investigator site in order to audit the study. The purpose of this visit is to check that the study is carried out according to Good Clinical Practices. Before conducting an audit, the monitor will contact the investigator in order to agree upon a mutually suitable date. The investigator and his team are required to cooperate with the auditors and to grant them access to the patients' medical files and to the study documents (CRFs and investigator's binders).

10.3 IRB and regulatory inspections

A regulatory authority may also wish to conduct an inspection (during the study or even after its completion). If an inspection is requested by a regulatory authority, the investigator must inform the sponsor and BI immediately that this request has been made.

The Principal Investigator must obtain IRB approval for the investigation. Initial IRB approval, and all materials approved by the IRB for this study including the subject consent form and recruitment materials must be maintained by the Investigator and made available for inspection.

11 Quality Control and Quality Assurance

Data from the CRFs are entered into the study database by Contract Research Organization staff following their own internal standard operating procedures that have been reviewed and approved by the sponsor.

Subsequently, the entered data are systematically checked by Data Management staff, using error messages printed from validation programs and database listings. Obvious errors are corrected by Data Management personnel. Other errors or omissions are entered on Data Query Forms, which are returned to the investigational site for resolution. The signed original and resolved Data Query Forms are kept with the CRFs at the investigator site, and a copy is sent to the sponsor so the resolutions can be entered into the database. Quality control audits of all key safety and efficacy data in the database are made prior to locking the database.

12 Ethics

12.1 Institutional Review Board

Before implementing this study, the protocol, the proposed informed consent form and other information to subjects, must be reviewed by a properly constituted Institutional Review Board (IRB). A signed and dated statement that the protocol and informed consent have been approved by the IRB must be given to the sponsor before study initiation. The name and occupation of the chairman and the members of the IRB must be supplied to the sponsor. Any amendments to the protocol, other than administrative ones, must be approved by this committee.

12.2 Informed consent

The investigator must explain to each subject (or legally authorized representative) the nature of the study, its purpose, the procedures involved, the expected duration, the potential risks and benefits involved and any discomfort it may entail. Each subject must be informed that participation in the study is voluntary and that he/she may withdraw from the study at any time and that withdrawal of consent will not affect his/her subsequent medical treatment or relationship with the treating physician.

This informed consent should be given by means of a standard written statement, written in non-technical language. The subject should read and consider the statement before signing and dating it, and should be given a copy of the signed document. If the subject cannot read or sign the documents, oral presentation may be made or signature given by the subject's legally appointed representative, if witnessed by a person not involved in the study, mentioning that the patient could not read or sign the documents. No patient can enter the study before his/her informed consent has been obtained.

The informed consent form is considered part of the protocol, and must be submitted by the investigator with it for IRB approval.

12.3 Declaration of Helsinki

The investigator must conduct the trial in accordance with the principles of the Declaration of Helsinki, which can be accessed via the website of the World Medical Association at http://www.wma.net/e/policy/17-c_e.html.

13 Data Handling and Record Keeping

The information resulting from the execution of the protocol will be coded into the eCRFs database.

The eCRFs must be filled out on a timely basis. The data will be monitored and verified.

Each eCRF will be signed and dated by the investigator or a co-investigator named by the former in each site and clinically responsible for the patient during the study.

Access to the eCRF will be by individual passwords & according to GCP recommendations.

The completed eCRFs data will be transferred by the eCRF operator to the sponsor & will be kept by them for at least 15 years.

14 Financing and Insurance

Financing and insurance will be addressed in the future in a separate agreement.

15 Publication Policy

Any formal presentation or publication of data from this trial will be considered as a joint publication by the investigator(s) and appropriate sponsor's personnel. Authorship will be determined by mutual agreement. It is a multicenter study, it is mandatory that the first publication is based on data from all centers, analyzed as stipulated in the protocol, by the sponsor statisticians, and not by the investigators. Investigators participating in multicenter studies agree not to present data gathered from one center or a small group of centers before the full publication, unless formally agreed to by all other investigators and the sponsor.

The investigator may be required to sign the clinical study report, if it is to be used in a registration submission to the health authorities of some countries. For multicenter studies, only the coordinating (principle) investigator nominated by the sponsor at the start of the trial would provide any needed signature.

References

Appendix 1 Diabetes medication titration

Researches will make an effort to prevent hypoglycemia events and worsening hyperglycemia at all stages of the study. All patients will receive an endocrinology consultation on diabetes medication titration prior to starting any study medication. Any changes in the diabetes treatment regimen are allowed apart from initiating SGLT2 inhibitors.

The consultation will include instruction to monitor fasting glucose closely on the first week of each period of the study, to make changes in medication doses upon initiation of each study period (including a specific recommendation for the washout period) and in any case that glucose is over 150 for 3 consecutive days (see details on specific medication below). This instruction will be repeated by the cardiologist on subsequent visits at the beginning of washout and at the beginning of the second treatment period. If at any point of the study fasting glucose is over 180 for 7 days despite taking the following measures – schedule emergency endocrinology consultation within a week.

Decision to titrate depends on patient glycemic control prior to study:

- A. Patients with HbA1c over 7.5% and fasting glucose usually over 150 with no hypoglycemia events or glucose measurements under 90 – no change in diabetes medications or insulin.

- B. Patients with fasting glucose usually under 150 or HbA1c under 7.5% - when oral medication (empagliflozin or placebo) is started reduce insulin by 20%, stop sulfonylurea and repaglinide, titrate as indicated below according to glucose measurements.

Basal insulin

If fasting glucose usually under 150 or HbA1c under 7.5% - reduce by 20% upon initiation of study medication. Otherwise no change.

Further titration by the patient throughout study:

If fasting glucose for 3 days is: Basal insulin should be changed by:

- >180 mg/dL → increase by 4 units
- >140 mg/dL → increase by 2 units
- <110 mg/dL → decrease by 2 units
- <100mg/dL → decrease by 4 units

If fasting glucose in even one measurement is low, reduce basal insulin:

- <90mg/dL → decrease by 4 units
- < 80 mg/dL → decrease by 6 units

Prandial insulin or insulin mixes

If preprandial noon/evening/bedtime glucose is under 100 - decrease all doses by 20%

If noon+evening+bedtime glucose is over 150 for 3 days – increase dose by 10%

Sulfonylurea

If fasting glucose under 150 mg/dL or HbA1c under 7.5% - stop

Then:

If fasting glucose over 150 for 7 days restart at half dose

If under half dose fasting glucose over 150 for 7 days - return to full dose

If anytime during study glucose under 90+symptoms or under 70 without symptoms – stop

Acarbose, DPP4 inhibitors, short acting GLP1 agonists

No initial changes

If hypoglycemia occurs (glucose under 90+symptoms or under 70 without symptoms) stop one medication in the following order: GLP1 agonist/DPP4 inhibitor, acarbose

Metformin

No initial changes.

If hypoglycemia only on Metformin and study drug – reduce Metformin to half the dose

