Evaluations consists of vital signs, laboratory assessments blood examination, device (ICD or CRTD/P) interrogation, 24h' Holter ECG in case of ICD/CRTD/P malfunction as a backup arrhythmia assessment and echocardiography. Patient's glucose level will be monitored by a home device 3 times a day in the first week and thereafter once a week or as needed. At visit 2, an endocrinologist consultant will give to the patient instructions for antidiabetic treatment titration according to [appendix 1](#).

Patients will be treated for up to 8 weeks with the study drug or placebo 10 mg/day every morning.

Washout period

Study subjects will stop study drug (empagliflozin/placebo) of the first treatment period and will be given placebo for a washout period of 4 weeks and will crossover to the second drug at the end of this period at the beginning of the next treatment period. During this period, patient's glucose level will be monitored by a home device 3 times a day in the first week and thereafter once a week or as needed. Safety laboratory examinations, HbA_{1c}, device interrogation and resetting, Holter ECG and echocardiography will be performed at the end of this period (visit 3). In the case of abnormal glucose levels during the washout period, diabetes treatment will be changed according to appendix 1 aiming to maintain glucose levels at normal range.

Second treatment period

Patients will crossover to empagliflozin or placebo treatment for a period of 8 weeks.

Evaluations consists of vital signs, laboratory assessments including pregnancy test for FCBP. Patient's glucose level will be monitored by a home device 3 times a day in the first week and thereafter once a week or as needed. Device (ICD or CRTD/P) interrogation and 24h' Holter ECG in case of ICD/CRTD/P malfunction as a backup arrhythmia assessment and echocardiography. In the case of abnormal glucose levels during the second treatment period, diabetes treatment will be changed according to appendix 1 aiming to maintain glucose levels at normal range.

Patients will be treated for up to 8 weeks with the study drug or placebo 10 mg/day every morning.

Medication compliance will be performed during the two treatment periods by counting the returned study drug blisters.

Accompanying scientific program

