4.2.1 Visit schedule and assessments

Table 2 visit schedule and assessments

Trial Period	Screening	Treatment Period			
Visit	1	2	3	4	5
Study Week	0	8	16	20	28
Days from randomization	-56	0	56	84	140
Informed Consent	X				
Inclusion/Exclusion Criteria	X	X			
Medical History	X				
Concomitant therapy	X	X	X	X	X
Demographics	X				
Physical Exam	X	X			
Vital Signs	X	X	X	X	X
Height	X				
Weight	X	X	X	X	X
Randomization		X			
Pregnancy test ¹	X	X		X	X
Home Blood glucose monitoring ²		X	X	X	X
Safety blood samples ³	X	X	X		X
HbA _{1c}	X		X		X
Device Interrogation	X	X	X	X	X
Monitor Counter Reset	X	X	X	X	X
12 Lead Holter ECG for 24hrs		X	X		X
Echocardiography	X ⁴	X	X		X
NT-Pro-BNP		X	X	X	X
Medication Compliance check			X		X

¹ For female patients with childbearing potential (Urine pregnancy test).

[figure not shown]
² Patients without means for daily home blood glucose monitoring will be given a device on visit 2. Glucose level will be measured 3 times a day in the first week and thereafter once a week or as needed. Additional measurements are warranted in the case of hypo- or hyperglycemia signs or symptoms.

³ Safety blood samples include: Fasting blood samples (8hr fasting), Liver and kidney functions, urine dipstick for signs of infection and ketoacidosis (if positive leukocyte esterase (WBC) or nitrites a midstream urine sample for urine culture will be taken.

⁴ Echocardiography will be done if needed to verify patient suitability for inclusion criteria.

Trial Period	Screening	Treatment Period			
Visit	1	2	3	4	5
Study Week	0	8	16	20	28
Days from randomization	-56	0	56	84	140
Endocrinologist consult		X			
Biobank samples		X	X	X	X
Urine Analysis (Electrolytes)		X	X	X	X
24hr Urine Sample collection		X	X	X	X
CardioPulmonary Exercise Test & 6 minute walk distance ⁵		X	X		X
Adverse events		X	X	X	X

Study scheme

Visit 3
Analysis 1

Visit 5
Analysis 2

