Collection of information on standard of care treatment will be done as part of medications records during the study.

17. Invite study subject to study site for Holter ECG installation in one of the 7 days before the next visit.

Base line visit (2) (day 0 ±7 days)

1. Patient's enrollment. Eligibility for the study according to inclusion and exclusion criteria will be rechecked but lab tests not repeated) if all criteria are fulfilled and there is no significant change in the subject's health, he/she will be enrolled into the study to receive the first study drug.
2. Get patient randomization number.
3. Begin study drug treatment (active or placebo), provide patient 60 tablets and give treatment instructions for home use.
4. Perform a complete physical examination.
5. Measure vital signs in order to ensure compliance with study criteria. Vital signs measurements will include systolic and diastolic blood pressure, pulse rate, respiratory rate, and body temperature. Body weight will also be measured. Measurements that may potentially constitute future adverse events (e.g. hypertension, fever etc.) should be graded in the medical history form at baseline according to CTC as described in [8.1.3 below](#)
6. Collect safety blood and urine samples. Including hematology and chemistry blood examinations and urine dipstick for signs of ketoacidosis or infection.
7. Review menopausal status and in women of childbearing potential perform a urine pregnancy test (β -HCG).
8. Collect home diary glucose results and provide a new diary for the following period.
9. Provide home diary for daily blood glucose determination.
10. Perform device interrogation.
11. Perform Monitor counter reset.
12. Collect Holter ECG device results and invite study subject to study site for Holter ECG installation in one of the 7 days days before the next visit.
13. Perform echocardiography for determination of EF
14. Consult endocrinologist for glucose lowering medication titration
15. Collect blood examination for NT-Pro-BNP
16. Collect urine and blood examination for biobank sample
17. Collect urine for electrolyte concentration

18. Obtain 24 hours urine sample collection
19. Perform cardiopulmonary exercise test (In case of inability to perform cardiopulmonary exercise test according to clinical judgment, patient will have a 6 minute walk distance test)
20. Perform 6 minute walk distance
21. Review concomitant medications.
22. Document adverse events.

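### After week 1 of each period, the once-weekly home glucose readings cannot supply the 3-day and 7-day runs that Appendix 1 relies on throughout the study

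*Combined protocol and SAP*

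**What the plan says.** **Monitoring.** The Synopsis and section 4.2 give the same home schedule in the first treatment period, the washout and the second treatment period: "3 times a day in the first week and thereafter once a week or as needed". Table 2 footnote 2 repeats it and adds: "Additional measurements are warranted in the case of hypo- or hyperglycemia signs or symptoms". The visit 2 list in section 4.2.2 reads differently: "Provide home diary for daily blood glucose determination". Appendix 1 asks patients to "monitor fasting glucose closely on the first week of each period of the study".

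**Rules.** Appendix 1 does not confine its titration rules to that first week.

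- The general instruction changes doses "in any case that glucose is over 150 for 3 consecutive days".
- The basal insulin table of 3-day fasting rules is introduced by "Further titration by the patient throughout study".
- For sulfonylurea: "If fasting glucose over 150 for 7 days restart at half dose". A further 7 days over 150 on half dose leads back to the full dose.
- The emergency consultation rule begins: "If at any point of the study fasting glucose is over 180 for 7 days despite taking the following measures".
- Prandial insulin or mixes go up when the noon, evening and bedtime values exceed 150 for 3 days.

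Other rules act on one value or event. These are basal insulin reductions below 90 or 80, the prandial decrease (no number of days stated), the sulfonylurea stop, and the hypoglycaemia rules for the remaining drugs.

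**The concern.** A rule that needs several days of readings works only if the schedule produces them. After week 1 it does not.

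The patients most exposed are those with fasting glucose usually under 150 or HbA1c under 7.5%. Appendix 1 cuts their insulin by 20% and stops sulfonylurea and repaglinide when study tablets start, whether active or placebo. In a placebo period they lose background therapy with no active drug in its place, and neither they nor the site knows it. Section 4.2 sends abnormal glucose in the washout and second treatment period to Appendix 1 for correction.

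Table 2 has no visit between days 0 and 56 or between days 84 and 140. Any Holter fitting in the week before a visit has no glucose check listed. Home readings are therefore the only scheduled glucose data in those intervals.

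**Working it through.** The plan gives no figure to reproduce, so the check lays the scheduled readings over the calendar and compares them with the rules.

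**Inputs.** Period lengths of 8, 4 and 8 weeks (section 4.2; Table 2 days 0, 56, 84, 140). Readings on each of 7 days, then one a week (section 4.2, Table 2 footnote 2). Rules from Appendix 1. Assumption: the weekly reading keeps the same weekday.

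**Step 1. Coverage.**

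| Period | Days | Daily-reading days | Other days | Weekly readings |
|---|---|---|---|---|
| First treatment | 56 | 7 | 49 | 7 |
| Washout | 28 | 7 | 21 | 3 |
| Second treatment | 56 | 7 | 49 | 7 |
| Total | 140 | 21 | 119 | 17 |

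21/140 = 15% and 119/140 = 85%.

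**Step 2. Runs available.** Within week 1, a 3-day run can end on 7 − 3 + 1 = 5 days (days 3 to 7) and a 7-day run on 7 − 7 + 1 = 1 day (day 7). The longest scheduled run is 7 days, or 8 if the weekly reading happens to abut a daily week. If the weekday may vary, the most is 1 + 7 + 1 = 9. No 3-day run lies wholly after week 1.

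**Step 3. Rules against runs (scheduled readings only).**

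| Rule | Days needed | Week 1 | After week 1 |
|---|---|---|---|
| General, over 150 | 3 consecutive | Yes | No |
| Basal insulin, up (over 180, over 140) or down (under 110, under 100) | 3 | Yes | No |
| Prandial or mix increase | 3, at three times of day | Yes, if readings are at those times | No |
| Sulfonylurea restart | 7 | Day 7 only | No |
| Sulfonylurea back to full dose | 7 + 7 = 14 | No | No |
| Emergency consultation | 7; or 3 + 7 = 10 if counted after a 3-day titration step | Only if the 7 days may overlap that step | No |
| Single-value low-glucose rules | 1 | Yes | Yes, on any reading taken |

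No scheduled run reaches 10 or 14 days. If sulfonylurea restarts on day 7 of the first treatment period, the next scheduled 7-day run ends on day 56 + 7 = 63. That is 56 days later, where the rule envisages 7.

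**Step 4. Looser reading.** Only the general over-150 rule states that the days are consecutive. If the other rules could be met by successive weekly values, 3 readings would span 2 × 7 + 1 = 15 days. Seven would span 6 × 7 + 1 = 43 days, longer than the 28-day washout.

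**Step 5. Time points.** Even in week 1, the prandial increase uses noon, evening and bedtime values while other rules use a fasting value. That is four time points against three readings a day.

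**The case against.** The case on the other side has real force on several points.

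- **The rules can fire.** Each period opens with a week of daily readings, which is when the initial insulin and sulfonylurea changes take effect. A reader might infer that the triggers can never operate; the documents do not support that.
- **Weekly is not a ceiling.** As-needed readings are allowed, and a patient could follow a high weekly value with daily testing. This stands only in part. Nothing says when a reading is needed or that a high value starts daily testing, and footnote 2 ties extra readings to signs or symptoms.
- **Hypoglycaemia.** A reader might infer that low values are missed as well. Most low-glucose rules act on one reading or event; only the two milder basal decreases (under 110, under 100) need 3 days.
- **Consistency of the schedule.** The Synopsis, section 4.2 and footnote 2 agree with one another, and Appendix 1 agrees on week 1. The odd item is the visit 2 diary wording, which is accurate for the week that follows that visit.
- **Backstops.** Diaries are collected at visits 2 to 5, fasting safety samples are taken at visits 2, 3 and 5, and HbA1c is measured at visits 3 and 5. Patients are reminded of their instructions at visits 3 and 4. Any change of diabetes regimen other than starting an SGLT2 inhibitor is allowed, so clinicians need not wait for a trigger. But clinicians must see values to act, and none are scheduled at the site within either 8-week treatment period. In Table 2, visit 4 has neither safety bloods nor HbA1c.

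**Conclusion.** The mismatch holds. Over 119 of the 140 days after randomisation (85%), scheduled readings cannot supply the runs that the multi-day rules require. The return of sulfonylurea to full dose cannot be completed within one period even with week 1 counted. What is left uncovered is asymptomatic hyperglycaemia after week 1, including in placebo periods after background therapy has been reduced.

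The result rests on counting scheduled readings only. The 10-day figure for the emergency consultation also assumes that its 7 days start after a 3-day titration step. The 85% is a share of calendar time; it does not estimate how many patients or triggers would be missed, and the documents give no basis for such an estimate.

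A reader might go further and infer that glycaemic control will drift between periods and bias the treatment comparison. The documents do not show this: the monitoring schedule is the same in both treatment periods. The sample size and the primary analysis are not at issue. This is a point of patient safety and internal consistency that should be settled, because stated safety rules cannot be evaluated from the readings the protocol requires.

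**What to change.** Reconcile the home monitoring frequency in the Synopsis, section 4.2, Table 2 footnote 2 and the visit 2 diary item with the multi-day rules in Appendix 1, so that each rule can be evaluated from readings the protocol requires. In the same edit:

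- state whether the 3-day and 7-day rules other than the general one mean consecutive days;
- state what makes an as-needed reading required;
- state which times of day the readings must cover.

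The choice of frequency, thresholds and rules is for the sponsor and its clinical advisers.

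The cost is protocol and diary wording, and possibly some extra home readings. Table 2 footnote 2 already provides a device to patients who lack one.

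### Appendix 1's basal insulin line gives no starting reduction to a patient above both glycaemic thresholds with a prior low, although group A withholds 'no change' from that patient

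*Combined protocol and SAP*

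**What the plan says.** Appendix 1 bases the starting decision on glycaemic control before the study.

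- **Group A** makes no change to any diabetes drug. It needs HbA1c above 7.5% and "fasting glucose usually over 150 with no hypoglycemia events or glucose measurements under 90".
- **Group B** is "Patients with fasting glucose usually under 150 or HbA1c under 7.5" per cent. When study medication starts, insulin is cut by a fifth, and sulfonylurea and repaglinide are stopped. A prior low is not a criterion.
- **Basal insulin, starting line:** for patients meeting either group B threshold, "reduce by 20% upon initiation of study medication. Otherwise no change".
- **Sulfonylurea, starting line:** "If fasting glucose under 150 mg/dL or HbA1c under 7.5% - stop". It has no clause for other patients, and it omits the word 'usually' that group B attaches to fasting glucose.
- **Basal insulin, on study:** "If fasting glucose in even one measurement is low, reduce basal insulin", by 4 units below 90 and 6 units below 80.
- **Sulfonylurea, on study:** "If anytime during study glucose under 90+symptoms or under 70 without symptoms", stop.

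The appendix opens with its aim: "Researches will make an effort to prevent hypoglycemia events and worsening hyperglycemia at all stages of the study". It also provides a safeguard: "All patients will receive an endocrinology consultation on diabetes medication titration prior to starting any study medication". Any change of regimen is permitted except adding an SGLT2 inhibitor.

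**The concern.** Group A's third condition is a safety condition: a patient with a prior low should not simply continue as before when a further glucose-lowering drug is added. No starting rule then acts on it. The two groups do not cover everyone, and the basal insulin line fills the gap with the very action that group A denies.

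At stake is avoidable hypoglycaemia when empagliflozin starts, in patients whose records already show a low. Section 2.6 says that a smaller dose of insulin or secretagogue may be needed with empagliflozin. Section 5.1 admits HbA1c from 7% to 12%, and section 5.2 does not exclude prior hypoglycaemia, so such patients can be enrolled. This is a participant-safety point.

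**Working it through.** There is no plan figure to reproduce. The check is of the decision rules, followed by simple dose arithmetic.

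**Step 1. Apply the rules as written.** Inputs: the group A, group B and basal insulin lines of Appendix 1. Take HbA1c 8.0% and fasting glucose usually 170, and vary only the prior low.

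| Prior low | Group A? | Group B? | Starting basal insulin |
|---|---|---|---|
| No | Yes | No | No change |
| Yes | No (fails third condition) | No (above both thresholds) | No change |

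Across HbA1c of 7.2, 7.5 and 8.0% crossed with usual fasting glucose of 140, 150 and 170 (nine combinations, each with and without a prior low), the prior low never alters the starting basal instruction. A patient with a prior low who meets either group B threshold is already reduced, so the gap is confined to those not below either one. Values of exactly 7.5% or 150 can also fall in neither group.

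**Step 2. The same reading before and during the study.**

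| Fasting reading | Before study, patient above both thresholds | On study |
|---|---|---|
| 85 | 0 units | −4 units |
| Below 80 | 0 units | −6 units |

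**Step 3. The other drugs for this patient.**

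- Sulfonylurea: the line is ambiguous. Because 'usually' is missing, a single fasting low could be read as meeting the stop criterion. A daytime reading of 65 without symptoms, with fasting glucose usually 170, does not meet it, yet on study that reading stops the drug.
- Prandial insulin and repaglinide: no starting instruction reaches this patient.
- Metformin, acarbose, DPP4 inhibitors and short-acting GLP1 agonists: no initial change for anyone, so group membership does not matter.

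**Step 4. Size of a 20% starting cut and time to reverse it.** Basal doses of 20, 40 and 80 units are assumptions. The up-titration steps are Appendix 1's: +2 units per three days above 140, +4 above 180. A treatment period is 56 days.

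| Dose | Cut (0.2 × dose) | Days at +2 per 3 days | Days at +4 per 3 days |
|---|---|---|---|
| 20 | 4 | 4/2 × 3 = 6 (10.7% of 56) | 4/4 × 3 = 3 (5.4%) |
| 40 | 8 | 8/2 × 3 = 12 (21.4%) | 8/4 × 3 = 6 (10.7%) |
| 80 | 16 | 16/2 × 3 = 24 (42.9%) | 16/4 × 3 = 12 (21.4%) |

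These are best cases. Section 4.2 and Table 2 schedule readings three times a day in week 1 only, then weekly or as needed. Seven days hold two complete three-day runs, which restore 2 × 2 = 4 units above 140 or 2 × 4 = 8 units above 180. Anything beyond that needs unscheduled readings. Sulfonylurea returns to half dose after 7 days above 150 and to full dose after 7 + 7 = 14 days (14/56 = 25%), again only if daily readings continue past week 1.

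**The case against.** The case against has real weight.

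- **The specialist is already there.** Every patient sees an endocrinologist before study drug, who may change almost anything. The advice must also cover dose changes at the start of each study period, so it extends to visit 4, when placebo-first patients first take empagliflozin and the cardiologist only repeats it. This stands and lowers the risk. It does not correct the line: had the intention been to leave these patients to the specialist, the basal instruction could have been silent, whereas it states a default.
- **Other rules may help.** Prandial or mixed insulin doses fall by 20% if a pre-meal or bedtime reading is below 100, and this is not marked as on-study only. Basal insulin also falls on study after three days below 110 or 100, ahead of any real low. Both stand, but neither makes the starting basal dose depend on the prior low.
- **The on-study rules are narrower than group A's condition.** An asymptomatic reading of 70 to 89 does not stop sulfonylurea, and a daytime 85 does not cut basal insulin. This stands. A reader might infer that the appendix treats every reading below 90 as a reason to act; it does not.
- **A broad repair would overreach.** Moving everyone outside group A into group B would cut all insulin and stop sulfonylurea and repaglinide for one asymptomatic daytime 88, perhaps at HbA1c 11%. The appendix has no restart rule for repaglinide, and it also aims to avoid worsening hyperglycaemia. This stands and limits the fix.
- **Pooled data show no excess with insulin.** Section 2.5 gives 19.5% hypoglycaemia with empagliflozin against 20.6% with placebo. Those figures do not describe this subgroup and are not used here in either direction.

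**Conclusion.** The point holds for basal insulin. The written default for a patient above both thresholds with a prior low is no reduction, which contradicts group A's own condition. For a fasting reading below 90 it also differs from the on-study rule: 0 units against 4, or 6 below 80. For sulfonylurea, prandial insulin and repaglinide the fault is a missing or unclear instruction, not a wrong one.

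Three stronger readings are tempting and are not supported:

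- That the prior low has no effect on any drug. Only the basal line gives this patient an explicit default that conflicts with group A.
- That these patients are denied a reduction. The consultation may order one.
- That the gap biases the efficacy result. The starting rules are the same whichever blinded treatment is given, and nothing in the documents shows an effect on the primary comparison.

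The conclusion rests on reading the appendix literally. The documents do not give the number of such patients, and it is not estimated. The change should be made because it is cheap and concerns safety; it is not a reason to hold the trial.

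**What to change.** **Basal insulin.** Replace the final no-change clause with two instructions. Group A: no change. Patients above both thresholds who, within a stated look-back (for example the 8-week screening period), had a hypoglycaemia event or a fasting glucose below 90: cut basal insulin by 20% when study medication starts, unless the endocrinologist documents a different starting dose.

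**Sulfonylurea.** Add that it is also stopped at the start if, in the same look-back, glucose was below 90 with symptoms or below 70 without them. This matches the existing on-study trigger.

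**Prandial insulin and repaglinide.** State that in these patients the endocrinologist decides at visit 2, and that the decision applies again at visit 4. It would be tidy to give the same route to anyone still in neither group: a value exactly at a threshold, a low older than the look-back, or only an asymptomatic daytime reading of 70 to 89.

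**Cost.** A few lines of Appendix 1 and no new test, since group A already requires prior lows to be reviewed. Patients without a meter receive one only at visit 2, so their look-back rests on reported events and clinic samples. The downside is temporarily higher glucose in the newly covered patients. It is limited by the up-titration steps, provided that readings are taken on consecutive days beyond week 1, and by the emergency consultation after seven days of fasting glucose above 180.
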